Please respond to all components of this item, or clearly indicate which components are not applicable.

Informed consent and all study procedures, other than neuroimaging, will be conducted at BL8.224 or remotely through secure video conferencing software (e.g. Zoom, Teams). Neuroimaging will be done at the AIRC. When informed consent is conducted remotely, DocuSign will be used to obtain signatures. Please see the next page for the assessment schedule.

Methods used to protect privacy: Deidentified data will be stored in REDCap – a self-managed, secure, web-based solution that is designed to support data collection strategies for research studies. Only researchers associated with the study will have access to any protected health information (PHI). This information will not be stored on REDCap. Identifying information will be kept in a separate password-protected file only accessible to the PI and the research team on a need-to-know basis. Data will be analyzed by group, and subjects will be identified only by a subject ID number to protect their confidentiality. Researchers will destroy the personal identifiers upon completion of data collection for the study.

Data analysis plan:

Aim 1: Determine the effect of cortisol on task-driven hippocampal activation using, for the first time, high-resolution (1.5 mm isotropic) fMRI of hippocampal subfields (i.e., DG/CA3, CA1, subiculum). The design is a two-period crossover with randomized order of treatment conditions, and the primary interest is in the treatment effect on hippocampal subfield activation, estimated as the within-subjects difference in hippocampal subfield activation between the hydrocortisone and placebo treatment conditions. The index of hippocampal subfield activation is a beta-weight of the contrast of the task-active condition vs. the control condition (e.g. novel vs. familiar in the Novelty Detection task and lure correct rejections vs. false alarms in the Mnemonic Discrimination task). We will use linear mixed effects regression to estimate the following model of DG/CA3 activation, Y_{ijk} , of the i^{th} subject in the j^{th} group in the k^{th} period, cast in a traditional longitudinal data setup.

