$Y_{ijk} = \mu_i + \beta_c C_{ijk} + \gamma_t T_k + \gamma_c (C_{ijk} - C_{ij0}) + \varepsilon_{ijk}$, where the subject-level mean $\mu_i = \mu + S_i$ is comprised of an overall mean μ and a random subject effect S_i , the time and treatment condition indicators are T_k and C_{ijk} , and ε_{ijk} represents a random residual effect. The corresponding between-subjects sub-model is $Y_{ij0} = \mu_i + \beta_c C_{ij0} + \varepsilon_{ij0}$, where the parameter β_c is identified with the initial condition assignment, which is synonymous with group assignment and therefore represents the carry-over effect. The corresponding within-subjects sub-model is $\Delta Y_{ij} = Y_{ij1} - Y_{ij0} = \gamma_t + \gamma_c (C_{ijk} - C_{ij0}) + (\varepsilon_{ij1} - \varepsilon_{ij0})$, where the parameter γ_c is identified with the change in assigned condition and therefore represents the treatment effect.

Aim 2: Determine the effect of cortisol on hippocampal subfield volume using high-resolution structural MRI. Using the same randomized regression approach described above we will assess mechanistic aim 2.

Aim 3: Assess changes in hippocampal NAA, Glu, Cho and ml with cortisol using ^1HMR S. Similarly, changes in spectroscopy will be assessed using the randomized regression utilized in the previous aims.

Aim 4: Determine the effect of cortisol on declarative and visuospatial memory. We will estimate the treatment effects on declarative memory using the same linear mixed model setup as the primary aim.

Aim 5: Examine whether sex, stress, early life adversity, age, physical activity, GCR number or sensitivity, or changes in sleep during cortisol administration, predict hippocampal CS response, as assessed by memory testing and neuroimaging. We will assess treatment moderation by sex, stress, early life adversity, age, physical activity, and changes in sleep using the modeling setup described in the primary aim with additional terms added to the model. To assess the moderation of a dichotomous variable (i.e., sex), a group indicator (male vs. female) will be added to the regression model (

Form A

IRB # STU 2018-0360

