$Y_{ijk} = \mu_i + \beta_c C_{ij0} + \gamma_t T_k + (\gamma_c + \gamma_{cf} F_i)(C_{ijk} - C_{ij0}) + \varepsilon_{ijk}$, where the overall treatment effect $\gamma_c + \gamma_{cf} F_i$ is allowed to depend on an indicator F_i of sex. For continuous variables, baseline levels will replace the indicator of sex. Continuous moderator analyses will be refined entering and, adjusting for changes in moderators over time by including baseline and longitudinal levels in the model as

$Y_{ijk} = \mu_i + \beta_c C_{ij0} + \beta_q Q_{ij0} + \gamma_t T_k + (\gamma_c + \gamma_{cq} Q_{ij0})(C_{ijk} - C_{ij0}) + \gamma_q (Q_{ijk} - Q_{ij0}) + \varepsilon_{ijk}$. Here, the overall treatment effect $\gamma_c + \gamma_{cq} Q_{ij0}$ is allowed to depend on baseline levels, and the term $\gamma_q (Q_{ijk} - Q_{ij0})$ adjusts for changes from baseline in the within-subjects sub-model.

Aim 6: Explore the effects of cortisol on resting state regional functional connectivity, and whole brain connectomics.

As discussed in the primary aim, the treatment effects on resting state functional connectivity will be assessed using a randomized regression in a traditional longitudinal cast. The key indices of interest will be overall measures of network integrity (e.g., degree, centrality, rich club architecture, etc.).

Aim 7: Explore the impact of depressive symptoms on memory and hippocampal structure, activation, connectivity and 1HMRS outcomes in response to hydrocortisone administration. Depression as a moderator will be assessed similarly to the moderators proposed in aim 5. However, a dichotomous indicator variable representing baseline group assignment (depressed vs. healthy control) will also be included in the model.

Sample size determination:

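### The Aim 1 full model attaches β_c to C_ijk where the rest of the plan requires C_ij0; fitted as printed, γ_c would not measure the drug effect

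*Combined protocol and SAP*

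**What the plan says.** All references are to section 4.a of the combined protocol and SAP, Data analysis plan.

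- **Design and estimand (Aim 1).** "The design is a two-period crossover with randomized order of treatment conditions". The treatment effect is "estimated as the within-subjects difference in hippocampal subfield activation between the hydrocortisone and placebo treatment conditions".
- **Full model (Aim 1).** "Y_{ijk} = \mu_i + \beta_c C_{ijk} + \gamma_t T_k + \gamma_c (C_{ijk} - C_{ij0", followed by the closing bracket and the residual. Here β_c multiplies the condition in the current period.
- **Between-subjects sub-model (Aim 1).** "Y_{ij0} = \mu_i + \beta_c C_{ij0} + \varepsilon_{ij0". The text ties β_c to the condition a participant was first assigned and calls it the carry-over effect.
- **Within-subjects sub-model (Aim 1).** "\Delta Y_{ij} = Y_{ij1} - Y_{ij0} = \gamma_t + \gamma_c (C_{ijk} - C_{ij0", again with the bracket and residuals following. β_c is absent, "where the parameter γ_c is identified with the change in assigned condition and therefore represents the treatment effect".
- **Sex-moderation model (Aim 5).** "Y_{ijk} = \mu_i + \beta_c C_{ij0} + \gamma_t T_k + (\gamma_c + \gamma_{cf} F_i)(C_{ijk} - C_{ij0". β_c now multiplies C_ij0. The continuous-moderator equation under Aim 5 does the same.

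Aims 2, 3, 4 and 6 print no equation and refer back to the Aim 1 approach. Aim 5 is described as the primary-aim setup with terms added.

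**The concern.** The Aim 1 full model and its own within-subjects sub-model cannot both be right. If β_c multiplies C_ijk, it does not cancel when the two periods are subtracted. It cancels only if it multiplies C_ij0, which is constant within a participant.

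The full model is the line an analyst would most naturally turn into code, and four other aims lean on it. Someone who fitted it literally and then read γ_c as instructed would be testing a quantity that contains no drug effect. The drug effect would appear under the coefficient that the plan calls carry-over.

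**Working it through.** **Inputs.** Two sequences, with periods k = 0 and 1: hydrocortisone first (C = 1, 0) and placebo first (C = 0, 1). From the sample size section: 168 completers, d = 0.34, effects of 0.08 (target) and 0.16 (previously observed), and 90% power. Not stated in the plan, so assumed here: two-sided α = 0.05, 84 participants per sequence, and within-person correlation ρ over a range.

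**The plan's own figure.** With d on the single-period SD, power = Φ(√N · d/√(2(1−ρ)) − 1.96). For N = 168 and ρ = 0: √168 = 12.96, 0.34/1.414 = 0.240, 12.96 × 0.240 − 1.96 ≈ 1.16, power 87.6%. At ρ = 0.25 it is 94.9% and at ρ = 0.5 it is 99.3%; ρ of about 0.08 gives 90%. The stated 90% can be neither confirmed nor rejected, and this point does not depend on it.

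**Step 1: difference the printed model.**
Y_ij1 − Y_ij0 = γ_t + (β_c + γ_c)(C_ij1 − C_ij0) + residuals.
The plan's sub-model has γ_c alone, so it does not follow from the full model as printed.

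**Step 2: solve the cell means.** Let τ be the drug effect, π the period effect, and λ the carry-over added in period 2 for those given hydrocortisone first.

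| Cell | True mean | Printed (β_c C_ijk) | With β_c C_ij0 |
|---|---|---|---|
| Hydrocortisone first, k = 0 | μ + τ | μ + β_c | μ + β_c |
| Hydrocortisone first, k = 1 | μ + π + λ | μ + γ_t − γ_c | μ + β_c + γ_t − γ_c |
| Placebo first, k = 0 | μ | μ | μ |
| Placebo first, k = 1 | μ + π + τ | μ + β_c + γ_t + γ_c | μ + γ_t + γ_c |

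Four means and four parameters (rank 4) give an exact solution:

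- Printed: β_c = τ. Then γ_t + γ_c = π and γ_t − γ_c = π + λ, so **γ_c = −λ/2**.
- With C_ij0: β_c = τ. Then γ_t + γ_c = π + τ and γ_t − γ_c = π + λ − τ, so **γ_c = τ − λ/2**.

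Numerically, with λ = 0, τ = 0.16 gives a printed γ_c of 0 against 0.16 with C_ij0, and τ = 0.08 gives 0 against 0.08. With τ = 0.08 and an illustrative λ = 0.04, the values are −0.02 and 0.06.

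**Step 3: how the two forms relate.** Because C_ijk = C_ij0 + (C_ijk − C_ij0), γ_c with C_ij0 equals printed β_c plus printed γ_c. The fitted values are identical; only the meaning of γ_c changes. With complete data, printed γ_c is half the difference in mean participant totals, placebo-first minus hydrocortisone-first. That is the usual carry-over contrast with its sign reversed.

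**Step 4: size under a literal fit.** Simulation by generalised least squares, 4,000 trials per setting, N = 168, τ = 0.34 SD, λ = 0. The correlations are assumptions, not figures from the plan.

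| Assumed ρ | Printed γ_c: mean, SE, rejects | With C_ij0: mean, SE, rejects |
|---|---|---|
| 0.08 | 0.00, 0.113, 5.0% | 0.34, 0.105, 90.8% |
| 0.5 | 0.00, 0.134, 4.9% | 0.34, 0.077, 99.4% |
| 0.8 | 0.00, 0.146, 5.3% | 0.34, 0.049, 100% |

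The standard errors agree with theory. At ρ = 0.5, printed: ½√(2(1 + 0.5) × 2/84) = 0.134; with C_ij0: ½√(2(1 − 0.5) × 2/84) = 0.077.

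A separate run of 200 trials, fitted as mixed models with a random subject intercept (assumed ρ = 0.5, period effect 0.1, no carry-over), gave printed γ_c a mean of 0.008 (Monte Carlo SE 0.009) with 5% rejection and β_c a mean of 0.32. With C_ij0, γ_c averaged 0.33 with 99% rejection.

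**The case against.** The strongest reply is that this is one subscript and that the surrounding text settles it. The within-subjects sub-model has no β_c, the prose ties β_c to first assignment, and Aim 5, described as the primary setup with terms added, prints C_ij0 in both of its equations. The available text was extracted from a PDF, so a k in place of a 0 could even be an extraction fault. Since the two forms are reparametrisations, no information is lost: a literal fit would show a large coefficient on current treatment, and a careful analyst would notice it.

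All of that stands, and it limits the claim. A reader might infer that the planned primary analysis will return a null result for a drug that works. The documents do not support that: it would require coding one line literally against the sub-model printed just after it. A reader might also infer that γ_c has expectation zero in every case. It does so only without carry-over; in general it is −λ/2. Nor does the plan give γ_c two verbal meanings across aims; it is described as the treatment effect throughout.

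What the reply does not remove is the contradiction itself. A prespecified primary model should not leave the analyst to choose between two equations.

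**Conclusion.** The concern holds as an internal inconsistency in the primary model. As given, the Aim 1 full model conflicts with its own within-subjects sub-model, with its description of β_c, and with both Aim 5 equations. The algebraic result (printed γ_c = −λ/2, with τ in β_c) does not depend on sample size, correlation or α. The rejection rates rest on the assumptions listed with them and only illustrate the algebra. The practical risk is conditional on the line being coded as printed, and the extracted subscript still needs checking. If the original page reads the same way, the line is wrong as written in the model on which Aims 2, 3, 4 and 6 rely, and it should be corrected before analysis.

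The subscript change does not settle the label on β_c. Even with C_ij0, β_c is the first-period difference between sequences, which is τ when there is no carry-over. Carry-over appears in β_c − γ_c = τ − (τ − λ/2) = λ/2.

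**What to change.** 1. Check the subscript in the Aim 1 full model against the original page.
2. If it reads as here, replace β_c C_ijk with β_c C_ij0.
3. In the within-subjects sub-model, write C_ij1 − C_ij0 in place of C_ijk − C_ij0.
4. State that γ_c from this model is the treatment effect for Aims 1 to 4 and 6 assuming no carry-over, and that it equals τ − λ/2 otherwise.

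Dropping β_c and fitting only period and current condition is not an interchangeable remedy. It gives the same treatment estimate only when every participant has both periods. The plan allows for attrition of 10% to about 20%, and first-period-only data would then inform the two models differently.

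The cost is one subscript in the full model, one in the sub-model, a sentence of text, and the matching line of code. Design, data collection and sample size are unaffected.

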STUDY PROTOCOL AND STATISTICAL ANALYSIS PLAN

Official title: Exploring the Effects of Corticosteroids on the Human Hippocampus using Neuroimaging

NCT number: NCT03896659

IRB Approved date: June 14, 2023

Form A

IRB # STU 2018-0360

PROTOCOL FORM / RESEARCH DESCRIPTION

If an item does not apply to your research project, indicate that the question is "**not applicable**" – do not leave sections blank

Click once on the highlighted entry in each box to provide your response. Click the item number/letter or word, if hyperlinked, for detailed instructions for that question. If your response requires inserting a table, picture, etc, you may need to first delete the box that surrounds the answer and then insert your table or other special document.

1. Purpose and objectives. *List the purpose and objectives:*

This study will, for the first time in humans, examine the effects of cortisol on specific hippocampal subfields using state-of-the art multimodal high-resolution neuroimaging methods. This research study is translational in nature and will advance our understanding of the effects of stress and cortisol on the brain. This is a non-treatment study. The researchers are interested in whether hydrocortisone (medication form of a stress hormone cortisol) influences the brains of depressed vs. non-depressed people differently. The researchers are also interested in whether there are differences in the effects of hydrocortisone between males and females. The study has both mechanistic and clinical aims. The aims are as follows:

Mechanistic Aim 1: Determine the effect of cortisol on task-driven hippocampal activation using, for the first time, high-resolution (1.5 mm isotropic) functional MRI of hippocampal subfields (i.e., DG/CA3, CA1, subiculum).

Mechanistic Aim 2: Determine the effect of cortisol on hippocampal subfield volume using high-resolution structural MRI.

Mechanistic Aim 3: Assess changes in hippocampal metabolites NAA, Glu, Cho and ml with cortisol using 1HMRSS (spectroscopy).

Clinical Aim 4: Determine the effect of cortisol on declarative and visuospatial memory.

Clinical Aim 5: Determine whether sex, stress, early life adversity, age, physical activity, GCR number or sensitivity, or changes in sleep during cortisol administration, predict hippocampal CS response, as assessed by memory testing and multimodal neuroimaging.

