Exploratory Aim 6: Explore the effects of cortisol on resting state functional connectivity using whole brain connectomic mapping.

Exploratory Aim 7: Explore the impact of depressive symptoms on memory and hippocampal structure, activation, connectivity and 1HMRSS outcomes in response to hydrocortisone administration.

2. Background.

- Describe past experimental and/or clinical findings leading to the formulation of your study.
- For research involving investigational drugs, describe the previously conducted animal and human studies.
- For research that involves FDA approved drugs or devices, describe the FDA approved uses of this drug/device in relation to your protocol.
- Attach a copy of the approved labeling as a product package insert or from the Physician's Desk Reference.

You may reference sponsor's full protocol or grant application (section number and/or title) or if none, ensure background includes references.

Please respond to all components of this item, or clearly indicate which components are not applicable.

a. Background

See grant application uploaded in section 4.1.3d of the Smartform. The background information can be found in Section 3 (Research Strategy, pages 68-69).

b. Current practice

N/A

3. Study Design.

Describe the study design (e.g., single/double blind, parallel, crossover, etc.) Consider inserting a scheme to visually present the study design.

The study involves a double-blind, placebo-controlled, crossover design of hydrocortisone in depressed and non-depressed (healthy controls) participants. Within each group (depressed and non-depressed), participants will be randomized to receive

Form A

IRB # STU 2018-0360

hydrocortisone or placebo for 3 days, followed by MRI and cognitive testing on day 3. Participants will then undergo a 25-day washout of study medication and will then, again, receive hydrocortisone or placebo for 3 days, followed by MRI and cognitive testing. The order in which participants will receive hydrocortisone vs. placebo will be randomized by a study statistician.

4. Research Plan / Description of the Research Methods:

4.a. Provide a **comprehensive narrative** describing the **research methods**.

- 1) Provide the **order in which tests/procedures will be performed**,
- 2) Provide the **setting** for these events and a description of the **methods used to protect privacy** during the study.
- 3) Provide the **plan for data analysis** (include as applicable the **sample size calculation**)

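### The model for the main treatment effect (Aims 1-4 and 6) leaves out the diagnostic group within which order is randomised; adding it is a low-impact, nearly free improvement

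*Combined protocol and SAP*

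**What the plan says.** Section 1 (Purpose and objectives) says the researchers want to know whether hydrocortisone "influences the brains of depressed vs. non-depressed people differently". Section 3 (Study Design) sets up the randomisation accordingly: "Within each group (depressed and non-depressed), participants will be randomized to receive" hydrocortisone or placebo first.

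The data analysis plan in section 4.a gives one mixed model for Aim 1. Besides the random subject effect and residual it contains the initial-condition (carry-over) term, period and change in condition: "the time and treatment condition indicators are T_k and C_{ijk". The word group in that model does not mean diagnosis, because the carry-over parameter "is identified with the initial condition assignment, which is synonymous with group assignment"; it means treatment order.

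The other aims reuse this model. Aim 2: "Using the same randomized regression approach described above we will assess mechanistic aim 2". Aim 3 refers back to the same regression. Aim 4 works "using the same linear mixed model setup as the primary aim". Under Aim 6, effects on connectivity "will be assessed using a randomized regression in a traditional longitudinal cast".

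Diagnosis appears only in exploratory Aim 7, which treats depression as a moderator in the way of Aim 5 and adds that "a dichotomous indicator variable representing baseline group assignment (depressed vs. healthy control) will also be included in the model".

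**The concern.** The factor within which order is randomised, and by which the investigators suspect the response may vary, is missing from the model that gives the main treatment effect. If the two diagnostic groups respond differently, the pooled model treats that systematic difference as noise. The average effect would then carry a standard error that is too large, an interval that is too wide and a test with less power than the data allow. In a sample that mixes two populations, a reader would also want the group-specific effects next to the average.

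**Working it through.** **Inputs from section 4.a, Sample size determination.** 168 completers, d = 0.34, stated power 90%; memory, 136 completers, d = 0.38; moderation d = 0.68; depressed versus control memory after corticosteroids, d = 1.1.

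**Assumptions.** Alpha, SD and within-person correlation are not given. I take two-sided 0.05 and read d in two ways: in SDs of the within-subject difference (s = 1), or in single-measurement SDs with zero within-person correlation (s = √2). The response difference D is in the same units as d. Diagnostic groups are 84/84 and order is balanced within each. The first printed equation attaches the carry-over parameter to C_ijk, while its sub-model and the Aim 5 models use C_ij0; I use C_ij0.

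**The plan's 90%.** It is not reproduced exactly. At d = 0.34 and N = 168, power is 99.2% for s = 1 and 87.2% for s = √2. A value of s = 1.352 gives 90%, so I also use that.

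**Model.** With X = ±1 for order and G = ±1 for diagnosis, the period difference is

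dY = period + X(τ + G·D/2) + e, SD(e) = s.

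A diagnosis difference in level is constant within a person and drops out of dY. With order balanced within diagnosis, the estimate of τ is the same with or without the diagnosis terms and its true variance is s²/N. Only the residual changes: without the interaction, the reported SE is inflated by about √(1 + D²/(4s²)).

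| D | s = 1 | s = √2 |
|---|---|---|
| 0.34 | √1.0289 = 1.014 | √1.0145 = 1.007 |
| 0.68 | √1.1156 = 1.056 | √1.0578 = 1.028 |
| 1.1 | √1.3025 = 1.141 | √1.1513 = 1.073 |

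**Power at d = 0.34, N = 168.** The estimate is normal and the residual sum of squares noncentral chi-square, with N − 2 = 166 df without the terms and N − 4 = 164 with them.

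| D | s = 1: without / with | s = √2: without / with | s = 1.352: without / with |
|---|---|---|---|
| 0 | 0.9923 / 0.9923 | 0.8725 / 0.8724 | 0.900 / 0.900 |
| 0.34 | 0.9916 / 0.9923 | 0.8694 / 0.8724 | 0.897 / 0.900 |
| 0.68 | 0.9895 / 0.9923 | 0.8602 / 0.8724 | 0.889 / 0.900 |
| 1.1 | 0.9838 / 0.9923 | 0.8396 / 0.8724 | 0.869 / 0.900 |

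The largest loss is 0.8724 − 0.8396 = 3.3 points.

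**Memory, d = 0.38, N = 136, D = 1.1.** 0.9844 against 0.9926 (s = 1) and 0.8425 against 0.8751 (s = √2), a loss of 0.8 to 3.3 points.

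**Simulation, 40,000 runs, D = 1.1.** For s = 1 the mean estimate is 0.340, the true SD of the estimate 0.077, and the mean reported SE 0.088 without and 0.077 with the terms. Coverage of the nominal 95% interval without the terms is about 97% (s = 1) or 96% (s = √2).

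**Unequal diagnostic split.** An equally weighted average of the two group effects has variance s²(1/n₁ + 1/n₂)/4. At 112/56 that is s²/149.3 instead of s²/168, and power at d = 0.34 (s = √2, D = 0) falls from 87.2% to 83.2%. With diagnosis centred at its sample mean, treatment and diagnosis by treatment are orthogonal, the variance stays s²/168, and power stays at 87.2%.

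**The case against.** The strongest reply is that Aim 7 already does this. It models depression as a moderator on memory, structure, activation, connectivity and spectroscopy, so its treatment effect is γ_c in one diagnostic group and γ_c + γ_cf in the other. That stands. A reader might infer that the differential-response question is left unanalysed; the documents do not support this. Estimating an average first and moderation second is a legitimate order of work. What remains is that the main model's residual ignores the interaction, and that no text says the group-specific effects will accompany the average.

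Second, randomising within diagnosis does not by itself require a diagnosis term in a crossover. That also stands for a level difference: with complete two-period data, adding the main effect left the estimate unchanged and moved its SE by at most 0.000002. A reader might infer bias or an invalid test; neither follows.

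Third, the benefit is conjectural. The 0.68 is the moderation size used for power. The 1.1 concerns memory only and may be a difference in level, in which case nothing is lost. No response difference is given for the imaging outcomes. This stands and limits the weight of the point.

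Fourth, adding the terms is not free under every coding. With a 0/1 indicator, γ_c becomes the effect in the reference group, and an equally weighted average loses precision if the groups are unequal in size. The per-group counts in the sample size section do not say whether they refer to diagnosis or to order, so equal diagnostic groups cannot be taken for granted. Centring diagnosis at its sample mean answers this.

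A reader might also compute a loss of about 10 points (0.872 to 0.775 at D = 1.1) by deflating the sample size by 1 + D²/4. That mixes single-measurement SDs for the treatment effect with difference SDs for D, and it treats the estimate itself as noisier, when only its reported SE is inflated.

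**Conclusion.** The point holds as a low-impact improvement, not as a threat to validity. The main model omits the randomisation stratum. The treatment estimate is unbiased when order is balanced within diagnosis, and a level difference does not matter. If response differs by diagnosis, the reported SE is about 1% to 14% too large and the test conservative, with 0 to about 3 power points lost at d = 0.34 and 168 completers.

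These sizes rest on two-sided 0.05, equal diagnostic groups, balanced order, and assumed response differences of 0.34 to 1.1 in the same units as d. If responses do not differ, there is no loss. The mismatch with the stated 90% power and the undefined per-group wording are separate matters and do not carry this conclusion.

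**What to change.** In the model for Aims 1-4 and 6, add diagnosis, diagnosis by treatment and diagnosis by period; Aim 7 already has the first two. Centre diagnosis at its sample mean, so that γ_c remains the average treatment effect in the enrolled sample and loses no precision if the split is unequal. State that the Aim 7 diagnosis-specific effects will be reported with confidence intervals beside that average and labelled exploratory. As a separate clarification, say whether the per-group counts in the sample size section refer to diagnosis or to treatment order.

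The cost is a few lines of SAP text and two within-subject degrees of freedom (166 to 164); diagnosis is already known for every participant. If responses do not differ, power at d = 0.34 and N = 168 changes by about 0.01 point. The downside lies in the group-specific estimates. At 84 per diagnosis their 95% half-widths are 0.22 against 0.15 for the average (s = 1), or 0.30 against 0.22 (s = √2), and reporting them across five aims multiplies comparisons, hence the exploratory label.

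### The Aim 1 model calls β_c the carry-over effect, but β_c is the first-period treatment effect

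*Combined protocol and SAP*

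**What the plan says.** Section 4.a (Data analysis plan, Aim 1) describes a two-period crossover in which the primary quantity is the within-subject difference between hydrocortisone and placebo. The mixed model is explained through two sub-models.

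- **Between subjects:** the first-period outcome Y_ij0 is regressed on the first-period condition C_ij0, "where the parameter β_c is identified with the initial condition assignment, which is synonymous with group assignment and therefore represents the carry-over effect".
- **Within subjects:** the change Y_ij1 − Y_ij0 is regressed on the change in condition, and "the parameter γ_c is identified with the change in assigned condition and therefore represents the treatment effect".

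No other carry-over parameter is defined. The model is then reused. For Aim 2: "Using the same randomized regression approach described above we will assess mechanistic aim 2". For Aim 4: "We will estimate the treatment effects on declarative memory using the same linear mixed model setup as the primary aim". Aims 3 and 6 refer back in the same way.

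The Aim 5 sex equation contains β_c C_ij0 and (γ_c + γ_cf F_i)(C_ijk − C_ij0). The treatment effect attached to γ_c "is allowed to depend on an indicator F_i of sex", while β_c is common to both sexes. The continuous-moderator equation has the same structure plus a β_q Q_ij0 term. Aim 7 follows Aim 5, with an indicator for depressed status added.

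One subscript differs. The full Aim 1 equation shows β_c multiplying C_ijk, whereas both Aim 5 equations show C_ij0.

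**The concern.** Carry-over is what the first course leaves behind in period 2, so a coefficient estimated from period 1 cannot measure it. Nor can k = 0 be a pre-treatment baseline. C_ij0 would then be constant and β_c not estimable, and the Assessment Schedule places MRI and spectroscopy only at Visits 3 and 5.

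Two things are at stake.

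1. A report that follows the label would describe a real drug effect as carry-over, and would read a small β_c as reassurance that there was none.
2. Keeping β_c common across moderator levels is reasonable if β_c is carry-over. It is wrong if β_c is a treatment effect, because a drug effect that differs by sex or depression also differs in period 1. That constraint biases the estimates for Aims 5 and 7.

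**Working it through.** The plan gives no figure for this point, so there is none to reproduce. The check solves the model against standard crossover cell means.

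**Inputs.** From the plan: the two-sequence, two-period design; the model equations; 168 completers and d = 0.34 (Sample size determination). Assumed: 1:1 order with 84 per sequence, single-period SD = 1, two-sided α = 0.05, and within-subject correlation ρ, which the plan does not give.

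**Step 1: cell means.** Let τ be the drug effect, π the period effect, λ hydrocortisone carry-over, σ a sequence difference, and δ a change in drug effect from period 1 to period 2.

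| Sequence | Period 1 | Period 2 |
|---|---|---|
| Hydrocortisone first | μ + τ + σ | μ + π + λ + σ |
| Placebo first | μ | μ + π + τ + δ |

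**Step 2: solve with β_c C_ij0.** Four mean parameters fit four cells exactly.

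- β_c = period-1 difference = τ + σ
- γ_c = ½[(π + τ + δ) − (π + λ − τ)] = τ + (δ − λ)/2
- 2(β_c − γ_c) = λ + 2σ − δ

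With σ = δ = 0, β_c = τ and γ_c = τ − λ/2. Carry-over enters γ_c and never β_c.

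| τ | λ | β_c | γ_c | 2(β_c − γ_c) |
|---|---|---|---|---|
| 0.34 | 0 | 0.34 | 0.34 | 0 |
| 0.34 | 0.2 | 0.34 | 0.24 | 0.20 |
| 0 | 0.5 | 0 | −0.25 | 0.50 |

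**Step 3: what reading β_c as carry-over would do (illustration only).** A test of β_c = 0 with 84 v 84 at d = 0.34 has noncentrality 0.34 × √(84/2) = 2.20 and rejects 59% of the time with no carry-over (noncentral t 0.591). In 20,000 simulated trials at ρ = 0.5 the rejection rates were 0.593 for τ = 0.34, λ = 0; 0.593 for τ = 0.34, λ = 0.2; and 0.048 for τ = 0, λ = 0.5.

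The 59% depends on the scale of d. If 0.34 is in units of the SD of the within-subject difference, the single-period effect is 0.34√(2(1−ρ)). The rate then runs from 0.40 at ρ = 0.7 to 0.88 at ρ = 0.

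**Step 4: moderation as printed.** Take σ = δ = λ = 0 and n subjects per sequence within each sex. Within a sex, var(β̂_c) = 2/n and cov(β̂_c, γ̂_c) = (1−ρ)/n. Let Δβ and Δγ be the sex differences in the unconstrained estimates. Forcing Δβ = 0 makes generalised least squares return

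γ̂_cf = Δγ − [(1−ρ)/2] Δβ.

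Both Δβ and Δγ estimate the same true moderation, so the expected ratio to truth is 1 − (1−ρ)/2 = (1+ρ)/2.

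| ρ | (1+ρ)/2 | ML fits as printed, N = 168 | ML fits with main effect and F_i × C_ij0 |
|---|---|---|---|
| 0.3 | 0.65 | 0.64 | 0.99 |
| 0.5 | 0.75 | 0.74 | 1.01 |
| 0.8 | 0.90 | 0.90 | 1.00 |

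The fits are random-intercept, 1,500 trials per setting. Adding only a sex main effect leaves the exact ratios unchanged. A continuous moderator with its main effect (omitting the γ_q change term) gave 0.67, 0.75 and 0.90.

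**Step 5: the subscript.** With β_c C_ijk taken literally and σ = δ = 0, differencing the two periods gives β_c + γ_c as the coefficient of the change in condition. That contradicts the within-subjects sub-model, which has γ_c alone. Solving the cells gives β_c = τ and γ_c = −λ/2. The between-subjects sub-model fits either form, so β_c is the first-period treatment effect in both.

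**The case against.** The strongest reply is that little follows from the label. The primary quantity is the within-subject effect, γ_c estimates it whatever β_c is called, the plan states no test or action rule for β_c, and a 25-day washout is planned. Aims 2, 3, 4 and 6 use the model for treatment effects and announce no carry-over conclusion. All of this stands. The Step 3 rates illustrate an unplanned test, and the λ values are chosen for illustration.

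The moderation bias is also conditional. It arises when both periods are fitted jointly with β_c common. The plan's own within-subjects sub-model, extended by the moderator, recovered the true 0.34 in simulation, against 0.22, 0.26 and 0.30 from the joint fit at ρ = 0.3, 0.5 and 0.8. The constrained fit has a smaller standard error, and type I error stays near 5%, so the power loss is less than the ratios suggest: at moderation 0.34, from 0.45 to 0.32, 0.60 to 0.49 and 0.94 to 0.91. At 0.68 it is smaller still (0.96 to 0.85 at ρ = 0.3). This also stands, but the plan says mixed regression will estimate the printed model, so the joint fit is the natural reading. The moderator indicators promised in the text do not remove the bias.

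Finally, the C_ijk subscript may be an artefact of reading the PDF. The case does not rest on it.

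**Conclusion.** The concern holds. β_c is the first-period treatment effect under either printed form of the model, and nothing in the plan redefines it. The primary estimate is unaffected by the label, provided C_ij0 is the intended regressor. Two consequences remain: any carry-over statement drawn from β_c would be wrong in both directions, and the moderation estimates in Aims 5 and 7 would be shrunk to (1+ρ)/2 of truth if the equations are fitted as printed. The shrinkage result assumes no carry-over, order balanced within moderator level, and a random-intercept fit; its size depends on ρ, which the plan does not state. This should be fixed before analysis.

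**What to change.** 1. In Aim 1, describe β_c as the first-period, between-subject treatment effect, keep γ_c as the within-subject treatment effect, and delete the carry-over claim.
2. Check the Aim 1 equation in the source file. If it does show C_ijk with β_c, change it to C_ij0.
3. If carry-over is to be reported, use 2(β_c − γ_c), the sequence difference in subject totals, with a 95% CI. Treat it as an estimate only, with no pre-test and no change of analysis. State that it is aliased with sequence and treatment-by-period effects (λ + 2σ − δ) and imprecise: SE = √(4(1+ρ)/84) = 0.25, 0.27 and 0.29 SD at ρ = 0.3, 0.5 and 0.8. State also that protection against carry-over rests mainly on the planned washout.
4. In the Aim 5 equations and the Aim 7 model, add moderator × C_ij0, and print the moderator main effect where it is missing.

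The cost is SAP wording, one subscript check and one interaction term. No new data are needed.
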